## LIST OF ABBREVIATIONS AND DEFINITION OF TERMS

The following abbreviations and special terms are used in this study Clinical Study Protocol.

---

| Abbreviation or special term | Explanation                               |
|------------------------------|---|
| AE                           | Adverse event                             |
| ALT                          | Alanine aminotransferase                  |
| AST                          | Aspartate aminotransferase                |
| BM                           | Bowel movement                            |
| BP                           | Blood pressure                            |
| BSS                          | Bristol Stool Scale                       |
| CMP                          | Complete metabolic panel                  |
| COWS                         | Clinical opioid withdrawal scale          |
| eCRF                         | Electronic case report form               |
| CSA                          | Clinical study agreement                  |
| CSP                          | Clinical study protocol                   |
| CSR                          | Clinical study report                     |
| DBP                          | Diastolic blood pressure                  |
| ECG                          | Electrocardiogram                         |
| ECRF                         | Electronic case report form               |
| EDC                          | Electronic data capture                   |
| EU                           | European Union                            |
| FDA                          | Food and Drug Administration              |
| GCP                          | Good clinical practice                    |
| GI                           | Gastrointestinal                          |
| GMP                          | Good manufacturing practices              |
| IB                           | Investigators brochure                    |
| IBS                          | Irritable bowel syndrome                  |
| ICF                          | Informed consent form                     |
| ICH                          | International conference on harmonization |
| I/E                          | Inclusion/exclusion                       |
| IP                           | Investigational product                   |
| IRB                          | Institutional review board                |

|         |  |
|---------|--|
| ITT     | Intent to treat  |
| MedDRA  | Medical dictionary for regulatory activity                                     |
| NRS     | Numeric rating scale   |
| OIC     | Opioid induced constipation  |
| PAC-QOL | Patient assessment of constipation quality of life                             |
| PAC-SYM | Patient assessment of constipation symptoms                                    |
| PI      | Principle investigator   |
| PR      | PR interval – time from onset of P wave to the onset of the QRS complex on ECG |
| PRO     | Patient reported outcome   |
| QD      | Once per day   |
| QRS     | QRS interval – time from beginning to the end of a QRS complex on ECG          |
| QT      | QT interval  |
| QTcF    | Fridericia corrected QT interval   |
| SBM     | Spontaneous bowel movement   |
| SAE     | Serious adverse event  |
| SBP     | Systolic blood pressure  |
| SDV     | Source document verification   |
| SUSAR   | Suspected unexpected serious adverse reaction                                  |
| TEAE    | Treatment emergent adverse event   |
| ULN     | Upper limit of normal  |
| US      | United States  |
| VEGF    | Vascular endothelial growth factor   |
| WOCBP   | Women of child bearing potential   |

## 1. INTRODUCTION

### 1.1 Background

The prevalence of pain in patients with cancer is 30% in all cancer patients, 59% of patients receiving anti-cancer treatment, and 64% to 87% in patients with advanced cancer [1, 2]. Opioids analgesics are the mainstay in the treatment of cancer patients with moderate to severe pain. Following pain management guidelines, opioids can provide adequate pain relief in 75% to 90% of patients with cancer pain [1, 3, 4]. However, opioid use is frequently associated with adverse effects, the most common and debilitating being opioid induced constipation (OIC) [4]. Opioids decrease the secretion of fluids into the gastrointestinal tract, increase constriction of sphincters, and increase non-propulsive activity leading to constipation. Over 64% of cancer patients experience OIC along with the debilitating effects of the cancer itself [5].

There are no set guidelines for the management of OIC, however, current treatment include laxatives, stool softeners, and, if necessary, reflex evacuation via enema. However, in 46% of patients these treatments are not effective [6, 7]. Furthermore, a number of the conventional therapeutic interventions are inconvenient and in some cases impractical. For example, debilitated patients may not be able to self-administer an enema, and a constipated patient with severely inflamed hemorrhoids or neutropenia would not be an ideal candidate for an enema. Although generally well tolerated, side-effects of these various treatments for constipation include bloating, cramps, abdominal pain, nausea, diarrhea, dehydration, and electrolyte imbalances. In addition, prescription and over-the-counter laxatives do not specifically target the opioid mediated mechanisms that are the cause of the constipation. Other treatments available include a subcutaneous injection of methylnaltrexone (approved in US, EU, and Canada for patients with advanced medical illness) and oral lubiprostone (approved in US for treatment of OIC in patients with chronic non-cancer pain). There is a major unmet need for a well-tolerated and efficacious orally-administered treatment option for OIC in cancer patients.

## **1.2 Research hypothesis**

The primary aim of this study is to test the hypothesis that naloxegol is tolerable and safe for the treatment of OIC in cancer patients with pain. The secondary aims are to determine whether efficacy can be detected compared to controls and whether a controlled study design is feasible in the population with cancer.

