## **1.3 Rationale for conducting this study**

Currently naloxegol is approved and marketed for OIC in non-cancer patients in the United States. As described in Section 1.1 patients with cancer pain have an unmet clinical need in the high prevalence of poorly controlled opioid-induced constipation. If naloxegol is found to be safe and effective, it would represent a significant therapeutic advance in the treatment of cancer-related opioid-induced constipation. Because patients with chronic pain in the context of active cancer often require relatively high opioid doses and have more severe medical comorbidities than non-cancer pain patients, a study that confirms the tolerability and safety of naloxegol treatment is needed. By augmenting these aims with a secondary aim focused on efficacy and incorporating design elements that can reveal an efficacy signal, this study has the potential to both confirm safety and provide essential preliminary data for the development of a definitive, adequately powered efficacy trial.

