## **1.4 Benefit/risk and ethical assessment**

For a full description of preclinical findings regarding naloxegol, please refer to the Investigator's Brochure (IB). In Phase I studies in healthy volunteers, in which single doses up to 1000 mg and repeated doses up to 500 mg/day were administered, there were no clinically significant changes in clinical laboratory parameters or electrocardiograms (ECGs). Preliminary evaluations of the results indicate that naloxegol does not have cardiac ventricular repolarization effects as assessed by QTcF. Of the 92 healthy volunteers who received naloxegol in Phase I, 2 subjects had a potentially clinically significant decrease in supine BP, as defined by a drop of 20 mmHg or greater in systolic blood pressure (SBP) to a level <90 mmHg and a concurrent drop of 10 mmHg or greater in diastolic blood pressure (DBP) to a level <50 mmHg. All of these events occurred at naloxegol dose levels of 100 mg, were transient, and resolved spontaneously. In a placebo-controlled Phase I repeated dose study, AEs of dizziness were reported by 66.7% of patients at the highest dose of naloxegol compared with only 25% of patients on placebo. However, dizziness was transient and resolved spontaneously without intervention.

In a Phase II study, in which doses of 5 mg, 25 mg, and 50 mg/day were evaluated against placebo, naloxegol decreased symptoms of OIC as measured by increases in spontaneous bowel movements (SBMs)/week in non-cancer patients receiving a wide range of opioid doses for pain. The reversal of OIC was dose-dependent across the dose range of 5 to 50 mg naloxegol studied. Naloxegol was well-tolerated in the Phase II study at 5 and 25 mg/day with the most commonly reported side effects being GI symptoms (abdominal pain, diarrhea, and nausea) in the 50 mg cohort. The frequency of any GI AE was 53% in the 25 mg/day group and 48% in the corresponding placebo group. Most of the AEs were rated mild or moderate. Rare cases of GI perforation associated with the use of methylnaltrexone in OIC have been reported in the post-marketing setting. Such cases of perforation tend to occur shortly after initiation with drug and appear to be more commonly reported in debilitated patients with multiple co-morbidities, particularly co-morbid conditions that might impair the local or global structural integrity of the

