### **5.1.1 Procedures for randomization**

Eligible patients will be randomized in blocks to receive either 25 mg naloxegol or placebo in a 1:1 ratio. Bottle numbers will be assigned sequentially as patients become eligible for randomization. The clinical research coordinator will contact the randomization coordinator at [REDACTED] to obtain the bottle number for the subject. Patients who discontinue early from study will not be replaced. If a bottle is allocated incorrectly there will be no attempt to be remedy the error once the study drug has been dispensed.

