# **10. EVALUATION AND CALCULATION OF VARIABLES**

## **10.1 Primary aims: tolerability and safety**

The primary aim of this pilot study is to assess the tolerability and safety of naloxegol 25 mg in the management of OIC in the cancer population. The secondary aims are to assess efficacy and feasibility. The primary endpoint for tolerability and safety will be the difference in AEs between study groups. The secondary endpoints for this aim will focus on pain-related variables.

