## **11.0 SAMPLE SIZE DETERMINATION AND STATISTICAL METHODS**

### **11.1 Determination of sample size**

This study has been designed to provide essential information about the potential viability and utility of a definitive adequately-powered superiority trial assessing the ability of naloxegol to provide better efficacy for OIC in cancer patients than current therapies. It is pilot trial with the primary aim of determining safety and tolerability of this drug in the medically ill cancer patient. A secondary aim is to determine whether an efficacy signal can be determined, and if so what the effect size is—information critical to the design of a larger trial. Finally, feasibility, as determined by the ability to recruit and conduct the study according to protocol, is another secondary aim.

As a pilot, sample size determination is not considered to be dispositive of the actual planned recruitment. The study has been planned to screen approximately 64 patients to obtain 44 randomly assigned patients—22 per group. Provided by an ██████████ statistician, this number per group would allow a detection of a group difference of  $0.58 \pm 90\%$  confidence interval at a 70% power and 10% type I error, using a 2 sided tests). This is based off of spontaneous bowel movements per week over 1-4 weeks in the Phase III study of naloxegol 25mg versus placebo in non-cancer patients.

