#### **11.2.1 Safety and tolerability analyses**

Adverse events will be classified by body system and preferred team and summarized by the number of patients with events per treatment group. AEs which in the opinion of the investigator are unequivocally due to the progression of a patient's underlying cancer may be analyzed and tabulated separately from other AEs. The number of TEAEs related to the study drug or probably related to the study drug will be compared across active drug and placebo. The number of these AEs mapped to the GI tract will be additionally analyzed. As noted, this analysis will be augmented by descriptive incidence data from the extension period.

The change from baseline in the mean daily opioid dose and mean NRS pain scores (average and worst per day) will be summarized by treatment group, and tested within each treatment group using one-sample t-tests.

All laboratory test results, vital signs (sitting BP and pulse), ECG results, respiratory rate, hematology and blood chemistry will be summarized for each treatment group using descriptive statistics and change from baseline.

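### The plan says it will test that naloxegol is safe and may confirm safety, but a between-arm AE difference in 22 patients per arm, with no margin, interval or bound, can only estimate that difference

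*Combined protocol and SAP*

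**What the plan says.** Section 1.2 gives the primary aim as "to test the hypothesis that naloxegol is tolerable and safe for the treatment of OIC in cancer patients with pain". Section 1.3 adds that "this study has the potential to both confirm safety and provide essential preliminary data" for a later efficacy trial.

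Section 10.1 defines the endpoint: "The primary endpoint for tolerability and safety will be the difference in AEs between study groups". Section 11.2.1 says how it will be used: "The number of TEAEs related to the study drug or probably related to the study drug will be compared across active drug and placebo". GI events among these are analysed additionally, and the extension period adds descriptive incidence data. No test, significance level, margin, confidence interval, acceptable excess or decision rule is given for AEs.

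Section 11.1 plans "to obtain 44 randomly assigned patients—22 per group", and section 5.1.1 allocates 1:1. The only sizing statement, "at a 70% power and 10% type I error, using a 2 sided tests", refers to spontaneous bowel movements per week, which belong to a secondary aim.

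Other sections are more modest. The formal objective in section 2.1 and the opening of section 10.1 both say that safety and tolerability will be assessed, and section 11.1 calls the study a pilot.

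**The concern.** An ordinary comparison of two arms asks whether AE rates differ. Failure to show a difference does not support safety unless the analysis also says how large an excess has been ruled out, through a margin or an upper confidence limit. The plan provides neither, so the claim in sections 1.2 and 1.3 has no analysis behind it. This holds whatever AE rate is assumed.

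The stakes lie in how the result would be read. Section 1.3 justifies the trial partly because cancer patients have more severe comorbidities than the non-cancer patients already studied. If the report takes its wording from sections 1.2 and 1.3, it could state that safety was confirmed from data compatible with a substantial excess of common AEs, and nothing in the plan tells the reader how large that excess could be.

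**Working it through.** **Inputs.** n = 22 per arm (section 11.1), 1:1 (section 5.1.1). AE rates from section 1.4: "The frequency of any GI AE was 53% in the 25 mg/day group and 48% in the corresponding placebo group". These are Phase II rates in non-cancer patients for any GI AE, not the related-or-probably-related events that section 11.2.1 compares; no rate for those is given. No AE significance level is stated, so two-sided 10% is borrowed from section 11.1, with 5% alongside. All 44 patients are assumed to contribute. Withdrawals are not replaced (section 3.1.3) and the retention goal is 80% (section 10.2.2), so real precision could be lower.

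**The plan's own figure.** There is none for AEs to reproduce. The 0.58 in section 11.1 concerns bowel movements and says nothing about the AE comparison. Its unit and SD are not stated, so it cannot be verified; that is a separate matter.

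**1. Chance that a true excess is non-significant.** Let X and Y be the numbers with an AE on placebo and naloxegol, X ~ Bin(22, 0.48) and Y ~ Bin(22, 0.48 + d). Power is the sum of P(X = x)P(Y = y) over all outcomes with p at or below alpha. The miss rate is 1 minus power.

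| True excess d | Power at 10%: chi-square / Fisher | Missed at 10% | Power at 5%: chi-square / Fisher | Missed at 5% |
|---|---|---|---|---|
| 20 points | 0.38 / 0.26 | 62% / 74% | 0.26 / 0.17 | 74% / 83% |
| 30 points | 0.68 / 0.54 | 32% / 46% | 0.54 / 0.42 | 46% / 58% |
| 35 points | 0.82 / 0.70 | 18% / 30% | 0.70 / 0.59 | 30% / 41% |

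**2. Precision of the risk difference.** Half-width of the 95% CI = 1.96 × sqrt[p1(1 − p1)/22 + p0(1 − p0)/22].

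- p1 = 0.53, p0 = 0.48: 1.96 × sqrt(0.01132 + 0.01135) = 1.96 × 0.1506 = 0.295. An observed 5-point excess would have limits of about −24.5 and +34.5 points.
- Both 0.20: 1.96 × sqrt(2 × 0.16/22) = 0.236.
- Both 0.10: 1.96 × sqrt(2 × 0.09/22) = 0.177.

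The 10% and 20% rates are assumptions, chosen because related events will probably be less common than any GI AE.

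**3. Events not seen at all.** With zero events in n patients, the one-sided 95% upper bound is 1 − 0.05^(1/n).

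- Randomised naloxegol arm, n = 22: 1 − 0.05^(1/22) = 12.7%. An event with a true 5% rate is unseen with probability 0.95^22 = 32%.
- Including the extension. If 80% of the placebo arm crosses over (the retention goal, used here as an assumption), 22 + 0.8 × 22 = 39.6, about 40 patients, receive naloxegol; the maximum is 44. The bound is 7.2% (n = 40) or 6.6% (n = 44), and a 5% event is unseen with probability 13% or 10%. This assumes the same 14-day rate in both periods, and the added exposure is uncontrolled.

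**The case against.** The best defence is that the limitation is largely disclosed. Section 11.1 calls the trial a pilot, says its sample size calculation is not decisive, and defers to a larger trial; section 1.3 speaks only of potential; sections 2.1 and 10.1 use the softer verb. All of this stands, and it excuses low power. It does not reconcile the wording of sections 1.2 and 1.3 with an analysis that has no bound on harm.

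A reader might infer that a non-significant AE comparison is the plan's pass rule, so that safety would be declared whether or not the drug does harm. The documents do not say so. Section 11.2.1 only summarises and compares, and safety also draws on pain scores, opioid dose, laboratory tests, ECG and vital signs. The defect is that no criterion is stated, not that a false one is.

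A reader might also infer that the design almost guarantees a null result. At two-sided 10%, an excess of 30 to 35 points would be found more often than not.

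Two further cautions stand. The 48% rate belongs to a different population and a different AE definition. And the 12.7% and 32% figures apply only to the randomised naloxegol arm; extension exposure improves the zero-event bound but does nothing for the comparison between arms.

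**Conclusion.** The point holds: sections 1.2 and 1.3 claim something the design cannot deliver. Twenty-two patients per arm can estimate an AE difference to within about 30 points either way at rates near 50%, or 18-24 points at rates of 10-20%. At a 48% placebo rate, a true 20-point excess would be non-significant in 62-74% of trials at two-sided 10% (74-83% at 5%); excesses of 30 to 35 points would be missed in about 18-46% at 10%. These sizes are illustrations that rest on the Phase II non-cancer rate, a borrowed significance level and full data from 44 patients. The documents do not say what excess would count as large. The conclusion that safety cannot be confirmed without a margin or bound does not depend on any of these assumptions.

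**What to change.** - **Sections 1.2 and 1.3:** adopt the assess wording of sections 2.1 and 10.1. Remove the statement that the trial tests whether naloxegol is tolerable and safe, and the statement that it may confirm safety.
- **Section 11.2.1:** report the naloxegol-minus-placebo difference in the proportion of patients with a treatment-emergent AE in the randomised period, with a 95% CI, for all events, for related or probably related events, and for GI events. Limit the conclusion to saying that excesses above the upper limit are excluded.
- **Section 11.1:** state the expected half-width together with the rate it assumes. Add that zero events would exclude rates above 12.7% in the 22 randomised naloxegol patients, or above about 6.6-7.2% descriptively if 40-44 patients are exposed once the uncontrolled extension is counted.

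The cost is wording in four sections and one set of intervals, with no extra patients, visits or data. The downside is that the stated claim becomes less favourable.

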## **1.3 Rationale for conducting this study**

Currently naloxegol is approved and marketed for OIC in non-cancer patients in the United States. As described in Section 1.1 patients with cancer pain have an unmet clinical need in the high prevalence of poorly controlled opioid-induced constipation. If naloxegol is found to be safe and effective, it would represent a significant therapeutic advance in the treatment of cancer-related opioid-induced constipation. Because patients with chronic pain in the context of active cancer often require relatively high opioid doses and have more severe medical comorbidities than non-cancer pain patients, a study that confirms the tolerability and safety of naloxegol treatment is needed. By augmenting these aims with a secondary aim focused on efficacy and incorporating design elements that can reveal an efficacy signal, this study has the potential to both confirm safety and provide essential preliminary data for the development of a definitive, adequately powered efficacy trial.

## **1.4 Benefit/risk and ethical assessment**

For a full description of preclinical findings regarding naloxegol, please refer to the Investigator's Brochure (IB). In Phase I studies in healthy volunteers, in which single doses up to 1000 mg and repeated doses up to 500 mg/day were administered, there were no clinically significant changes in clinical laboratory parameters or electrocardiograms (ECGs). Preliminary evaluations of the results indicate that naloxegol does not have cardiac ventricular repolarization effects as assessed by QTcF. Of the 92 healthy volunteers who received naloxegol in Phase I, 2 subjects had a potentially clinically significant decrease in supine BP, as defined by a drop of 20 mmHg or greater in systolic blood pressure (SBP) to a level <90 mmHg and a concurrent drop of 10 mmHg or greater in diastolic blood pressure (DBP) to a level <50 mmHg. All of these events occurred at naloxegol dose levels of 100 mg, were transient, and resolved spontaneously. In a placebo-controlled Phase I repeated dose study, AEs of dizziness were reported by 66.7% of patients at the highest dose of naloxegol compared with only 25% of patients on placebo. However, dizziness was transient and resolved spontaneously without intervention.

In a Phase II study, in which doses of 5 mg, 25 mg, and 50 mg/day were evaluated against placebo, naloxegol decreased symptoms of OIC as measured by increases in spontaneous bowel movements (SBMs)/week in non-cancer patients receiving a wide range of opioid doses for pain. The reversal of OIC was dose-dependent across the dose range of 5 to 50 mg naloxegol studied. Naloxegol was well-tolerated in the Phase II study at 5 and 25 mg/day with the most commonly reported side effects being GI symptoms (abdominal pain, diarrhea, and nausea) in the 50 mg cohort. The frequency of any GI AE was 53% in the 25 mg/day group and 48% in the corresponding placebo group. Most of the AEs were rated mild or moderate. Rare cases of GI perforation associated with the use of methylnaltrexone in OIC have been reported in the post-marketing setting. Such cases of perforation tend to occur shortly after initiation with drug and appear to be more commonly reported in debilitated patients with multiple co-morbidities, particularly co-morbid conditions that might impair the local or global structural integrity of the

GI tract (eg, cancer, peptic ulcer, pseudo-obstruction of the colon, etc). Therefore, exclusion criteria have been included in this protocol to minimize entry of patients who may be predisposed to GI perforation. In addition, any patient who reports progressive or persistent severe abdominal pain is to be evaluated immediately by the site or otherwise referred for urgent medical assessment. Additional potential risk factors include ovarian cancer or the use of vascular endothelial growth factor (VEGF) inhibitors (eg, bevacizumab, sorafenib). See Section 4.2. No reversal of analgesia was seen at any dose in Phase II trials, as measured by changes in the daily opioid dose or by Numeric Rating Scale (NRS) for pain. Although these data suggest that the risk for reversal of analgesia or precipitation of opioid withdrawal is unlikely, pain will be monitored during this study.

Overall clinical safety data do not indicate that administration of naloxegol has adverse effects on the central nervous, renal, respiratory, or cardiovascular system. However, as summarized above, participation in this study may carry some risks. General safety monitoring, including AEs, vital signs, and clinical laboratory assessments combined with exclusion of patients at higher risk for complications from experimental medication and placebo are in place to minimize any risks. ECGs will also be recorded at visits 1 and 3.

There may be no benefits to patients as a result of participating in this study; alternatively, randomization to the active treatment group may provide symptomatic relief from OIC for the duration of the study. All patients will have the opportunity to take active drug during the 2-week open label phase of the study, provided they meet the relevant eligibility criteria. The results of the study may ultimately help in the development of naloxegol for treatment of OIC in patients experiencing cancer pain.

